We hypothesize that it will be feasible to recruit participants into a controlled trial, to evaluate and follow study participants and to preliminarily assess the efficacy of CALM in individuals with brain cancer. Preliminary information on CALM feasibility will be collected with regards to the ability to consent patients to the study, study session attendance, post-session assessment and follow-up assessment completion, and participant satisfaction ratings.

RESEARCH STRATEGY AND FEASIBILITY

Approach. A mixed-methods approach, utilizing the NIH Science of Behavior Change (SOBC) supported ORBIT model^{43,44} has been chosen for this study. The ORBIT model begins with a theory grounded in behavioral science about the mechanisms of behavior change (Phase I), and develops an intervention in small incremental steps, paying attention to tailoring, acceptability, and testing efficacy of early outcomes using smaller experiments (Phase II), before embarking on a randomized controlled trial (Phase III).

Study Population. Diagnosis and classification of brain cancer will be based on 2016 World Health Organization

revised criteria.⁴⁵ At VCU, 160 individuals with PBT are treated annually. For individuals with PBT, most are White (76%) followed by African American (16%) and most are men (59%). The majority fall into the younger age range (59%; 18-54 years).

Inclusion Criteria. This study will consider for enrollment individuals of all genders, ethnic, racial, and socioeconomic backgrounds. PBT participants must: (1) have a confirmed malignant brain cancer diagnosis via histopathology, (2) be a minimum of 2 weeks post-surgical resection or biopsy (if applicable), (3) be primarily English speaking, (4) be age 18+, (5) obtain ≥ 20 on Telephone Interview for Cognitive Status, (6) have current elevated depression (Patient Health Questionnaire-9 Item [PHQ9] ≥ 10) or death anxiety symptoms (Death and Dying Distress Scale [DADDS] ≥ 15),²³ and (6) have reliable internet connection.

Exclusion Criteria. This study will exclude participants with: (1) Major communication difficulties as determined by the research team which would prohibit psychotherapeutic interaction, (2) inability to meet with interventionist via an electronic device for telehealth intervention sessions, or (3) inability to provide informed consent.

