VCU Recruitment. VCUHealth treats approximately 160 individuals with PBT annually. Participants will be directly referred by their neuro-oncology clinical team. Flyers will also be posted in treatment rooms. If patients are interested in participating, a telehealth screening interview will be scheduled. Trained study staff will screen for eligibility. If eligible, individuals will have the study described to them. Interested individuals will be emailed and asked to read the consent form and encouraged to ask any questions. They will be informed that their decision to (or not) participate will not affect their care at any VCU facility. Once all questions are answered, interested individuals will be asked to sign the consent form electronically. We anticipate participation rates similar to those reported in prior advanced cancer behavioral health and psychotherapeutic trials, with $\geq 70\%$ consenting to screening and $\geq 30\%$ of eligible patients enrolling (**Table 1**).^{23,35,36,40,41}

Scientific Rigor. To parallel the multi-phase drug development scientific process, including intervention development and dose-response testing (Phase I), feasibility and acceptability evaluations (Phase II), and eventual Phase III efficacy trials, the NIH SOBC ORBIT model was selected to guide this project (**Figure 5**).⁴³ To promote a robust and unbiased approach, we will: (1) use validated measures (**Table 2**), (2) have a non-clinical research assistant (RA) conduct eligibility screening and consent to reduce coercion, and (3) have the RA collect participant measures and conduct exit interviews.

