AIM 1: Proof-of-Concept Trial Design. Using the ORBIT model, we will initially conduct a 1-year Phase IIa *Proof-of-Concept Trial* (N=12) to guide CALM implementation for individuals with PBT. Within one week before and after the intervention and 3 months post-intervention (if applicable given terminal illness; **Figure 6**), participants will be asked to complete self-report surveys of behavioral and psychological variables (**Table 2**) via a secure online data collection system (REDCap). Participants will be offered a \$20 gift card for completing these surveys across each of the 3 timepoints (pre-intervention, post-intervention, follow-up). If paper copies of the questionnaire are preferred by the participant, these can be mailed and the RA will input any data into REDCap upon return. Six sessions of CALM therapy will be provided at no cost to participants. After each intervention session, participants will be sent a link for a brief post-session satisfaction survey via secure email link. Participants will rate 1) topic applicability; 2) perceived benefit of session; 3) comfort with interventionist(s); and 4) overall satisfaction. Participants who withdraw will be contacted and asked open-ended questions on reasons for termination and suggestions for improvement. Interventionists will also complete surveys at the end of each session which address: 1) topic applicability; 2) perceived participant response; 3) suggestions for improvement.

Within one month of intervention completion, the RA will conduct individual exit interviews by phone (**Figure 8**), which will be audio recorded for verbatim transcription. Interviews will assess length and number of sessions, content applicability, recommended modifications, helpful and unhelpful aspects of sessions, perceived benefits, overall satisfaction, and suggestions for improvement. This will inform treatment preferences, intervention adaptations, and overall satisfaction. Our team has used these survey and interview measures with success in prior

treatment development trials.^{49,50} At any time during the intervention, participants considered by the therapist to be at acute risk for suicide, or who demonstrate significant worsening of depression or other psychiatric comorbidities that require treatment, will be referred for psychiatric assessment and treatment in the Department of Psychiatry. This may include pharmacotherapy or other psychiatric interventions.

[figure not shown]

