Figure 6. AIM 1 Intervention Timeline

CALM Interventionists. The PI has attended four international CALM advanced training workshops (2018: Toronto; 2019: London and Banff; 2020: Virginia). The PI is CALM certified and receives ongoing supervision from CALM founder on a bi-weekly basis to discuss cases, therapeutic fidelity, supervision of interventionists, and research procedures. The PI will supervise implementation of the CALM intervention by psychology post-doctoral and doctoral trainees. All interventionists will also have attended at least one 3-day CALM training workshop and participate in ongoing weekly supervision.

Assessment Measures.

Covariates. Baseline self-report data will include: age, gender, ethnicity, race, educational status, employment, marital and parental status, history of substance abuse and/or mental health history (psychiatric diagnoses, suicidal ideation), and self-reported social support and spirituality beliefs. We will extract the following data from medical records: time since diagnosis, tumor characteristics and treatment, seizure history, and psychopharmacological medication history. Patients' oncologists will report on estimated prognosis. Additional psychological intervention (e.g., psychotherapy, pastoral care, social work) and/or psychopharmacological medication use will also be tracked throughout the intervention and follow-up time period.

Table 1. Primary Outcomes

Feasibility*	
Recruitment	$\geq 70\%$ consent to screening; $\geq 30\%$ of eligible enroll
Eligibility	Reasons for ineligibility, reasons for refusal, characteristics for refusers
CALM intervention	$\geq 60\%$ session attendance; $\geq 70\%$ post-session assessments completed; $\geq 60\%$ follow-up assessments completed
Acceptability*	
CALM intervention	Session ratings of: satisfaction, helpfulness, enjoyment, relevance, utility (Likert Scale; 1=not at all, 5=very much; M ≥ 4 post-session surveys); overall program satisfaction (M ≥ 4); $\geq 75\%$ would recommend program to others (post-intervention survey); likes, dislikes, adaptations, future suggestions (exit interview)

Note. M = mean; *based on CALM trial data^{23,35,36} and additional intervention studies of patients with advanced disease⁴⁰⁻⁴²

Table 2. *Exploratory Outcomes*

Variable	Measurement	Minutes to Complete
Depression	Patient Health Questionnaire – 9 Item (PHQ9) ^{33*}	2 – 5
Generalized Anxiety	Generalized Anxiety Disorder – 7 Item (GAD7) ^{34*}	2 – 5

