Death Distress	The Death and Dying Distress Scale (DADDS) ^{35*}	5 – 10
Fear of Cancer Recurrence	Fear of Cancer Recurrence - 7 Item (FCR7) ³⁶	2 – 5
Attachment	Experiences in Close Relationships Inventory (ECR-M-16) ^{37*}	5 – 10
Quality of Life	Quality of Life at the End of Life-Cancer Scale (QUAL-EC) ^{38*}	5 – 10
Suicidal Ideation	Patient Health Questionnaire – Item 9 (PHQ9) ^{33*}	--
Clinical Evaluation	Clinical Evaluation Questionnaire (CEQ) ^{39*}	2 – 5

Note. *Measures used in the CALMRCT

DATA ANALYSIS.

Primary Outcomes. Detailed records of the number of individuals who screen, are eligible, enroll, complete assessment measures, and attend telehealth sessions will be kept. Reasons for attrition will be recorded. Individuals who “no-show” will be contacted to assess continued interest and will be rescheduled as appropriate. Each attempt to contact participants will be recorded. This information will guide future recruitment/retention and inform feasibility. Recruitment source will be tracked to determine the most fruitful strategies. We will calculate frequencies and proportions to explore preliminary feasibility outcomes and means and standard deviations or medians and interquartile ranges to assess preliminary acceptability (**Table 1**). The two-sample t-tests and/or Mann-Whitney U-test, and chi-square tests will be used to compare eligible patients who did and did not enroll in terms of demographic, medical, and psychiatric variables.

Exploratory Outcomes. Within-group changes in behavioral and psychological variables will be explored to prepare for future pilot and efficacy trials. Thus, for each data collection time points we will calculate the mean and standard deviation of exploratory outcomes. In addition, we will calculate the correlation on the measures between time points as well as calculating the difference scores and the accompanying standard deviations.

POTENTIAL CHALLENGES AND SOLUTIONS

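### Enrolled and non-enrolled eligible patients are compared only by significance tests, which at 12 v about 28 detect only very large differences; differences with confidence intervals should be the main output (minor).

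*Combined protocol and SAP*

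**What the plan says.** The comparison is set out in one sentence of DATA ANALYSIS, Primary Outcomes. Continuous variables get two-sample t-tests and/or Mann-Whitney tests. For categorical variables, "chi-square tests will be used to compare eligible patients who did and did not enroll in terms of demographic, medical, and psychiatric variables". No exact test, continuity correction, significance level, effect size, confidence interval or rule of interpretation is given.

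The same paragraph plans frequencies and proportions for the feasibility outcomes, and Table 1 lists the characteristics of refusers under feasibility. Descriptive counts are therefore foreseen, but the tests are the only stated method for setting the two groups against each other.

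The sample size is in AIM 1: Proof-of-Concept Trial Design ("N=12) to guide CALM implementation for individuals with PBT"). VCU Recruitment and Table 1 set the enrolment mark at 30% or more of eligible patients. Study Population gives the case mix: "most are White (76%) followed by African American (16%) and most are men (59" per cent), and "The majority fall into the younger age range (59%; 18-54 years").

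**The concern.** A feasibility study should show whom recruitment misses, and the plan says its recruitment records are to guide later recruitment and retention. With 12 enrolled patients, p-values alone serve that purpose badly. Some categorical tables will have expected counts well below 5, where the chi-square p-value can differ noticeably from the exact one. More importantly, the tests have little power, so most real imbalances would come out as not significant, and nothing in the plan tells the reader how to take that. A recruitment process that under-enrols a group could go unremarked in the reported comparison and be carried into the next trial.

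**Working it through.** **Inputs.** Enrolled: 12 (AIM 1). Enrolment: at least 30% of eligible patients (Table 1), a floor and not a forecast. Mix: White 76%, African American 16%, so other race 100 − 76 − 16 = 8%; men 59%, so women 41%; age 18–54 59%, so 55 and over 41% (Study Population). Assumed, because the plan is silent: two-sided 5% level, Pearson chi-square without continuity correction, and an eligible pool with the stated mix. The plan gives no power or precision figure for this comparison, so there is none to reproduce.

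**Group sizes.** Non-enrolled = 12/r − 12. At r = 0.30: 40 − 12 = 28. At 0.40: 18. At 0.50: 12. If only 25% enrol: 36.

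**Expected counts at 12 v 28** (group size × prevalence):

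| Category | Among 12 | Among 28 |
|---|---|---|
| White | 9.12 | 21.28 |
| African American | 1.92 | 4.48 |
| Other race | 0.96 | 2.24 |
| Women, or age 55+ | 4.92 | 11.48 |

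Counts of 1–2 are confined to the minority race categories. Sex and age fall just short of 5.

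**Error rate**, by full enumeration of two independent binomials at 12 v 28:

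| Prevalence in both groups | Pearson | Fisher |
|---|---|---|
| 8% | 4.4% | 1.0% |
| 16% | 4.5% | 2.0% |
| 24% | 4.7% | 2.8% |
| 41% | 5.6% | 3.3% |

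The Pearson maximum over all prevalences is 5.6%; for race in three categories its size is 3.9%. At other group sizes the maximum is 6.4% (12 v 12), 5.3% (12 v 18) and 5.5% (12 v 36).

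**Single tables.** For 2/12 v 0/28, Pearson's statistic is 40 × (2×28 − 10×0)² / (12 × 28 × 2 × 38) = 4.91, p = 0.027. The exact p-value is C(12,2)/C(40,2) = 66/780 = 0.085, about three times larger. For 3/12 v 1/28 the pair is 0.038 and 0.073; for 4/12 v 2/28 it is 0.034 and 0.055. Of the 13 × 29 = 377 possible tables, 20 are significant by Pearson and not by Fisher; none goes the other way.

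**Power at 12 v 28** (enrolled v non-enrolled):

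| True proportions | Pearson | Fisher |
|---|---|---|
| 0% v 16% | 7% | 3% |
| 32% v 16% | 23% | 17% |
| 21% v 41% | 22% | 15% |

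For 80% power by Pearson, the enrolled proportion must reach about 60% against 16%, or 86% against 41%: gaps of 44–45 points. For a continuous variable the 80%-power difference is (1.96 + 0.84) × √(1/12 + 1/28) = 2.80 × 0.345 = 0.97 SD, or 0.99 SD with the t distribution.

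**What an interval would show.** The half-width for a difference is 1.96 × √[p(1−p)(1/12 + 1/28)]: 25 points at p = 0.16 and 33 points at p = 0.41. Suppose 6 of 40 eligible patients are African American and none enrols. Then 0/12 v 6/28 is a difference of −21 points, Newcombe 95% CI −40 to +5, with Pearson p = 0.08 and Fisher p = 0.15. The interval shows that a large shortfall is compatible with the data; the p-value alone does not.

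**The case against.** Four points on the other side carry weight.

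- A reader might infer that chi-square p-values are unreliable throughout. The enumeration does not support that: the error rate stays close to 5%, and Fisher's test lies further from nominal with less power. Several of the 20 discordant tables are not sparse (6/12 v 5/28, for example) and largely reflect Fisher's conservatism. With Yates' correction, which the plan neither requires nor rules out, none of the 20 is significant. This stands; what remains is a caution about individual sparse tables.
- A reader might infer that the plan treats non-significance as proof that the sample is representative. It says no such thing and gives no interpretation rule. It leaves that reading open.
- A reader might count the Covariates list in Assessment Measures and infer a large overall false-positive rate. The documents do not say that those items are collected from patients who decline, the analysis sentence names only three broad domains, and such variables are not independent. No overall figure can be supported.
- Enrolling none of 6 African American patients among 40 happens by chance in 9.8% of random draws of 12, so not flagging it at 5% is correct behaviour for a test. That is so, and it is also why a test is the wrong main output for this question.

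Finally, the thresholds in Table 1 do not rest on these tests, and this is a 12-patient proof-of-concept study. This limits the severity but does not make the comparison informative as planned.

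**Conclusion.** The point holds as a minor one. The only stated method for comparing enrolled with non-enrolled eligible patients is a set of significance tests with about 7–23% power for differences of 16–20 points. They are likely to detect only differences of about 45 points or 1 SD, so a non-significant result cannot show that the groups are alike. Sparse-cell distortion is secondary: p-values in single tables can be roughly two to three times too small, while the overall error rate is at most about 5.6% at 12 v 28.

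These figures assume enrolment exactly at the 30% floor, the Study Population mix among eligible patients, a two-sided 5% level and no continuity correction. Higher enrolment would shrink the comparison group; lower enrolment, or the extra recruitment allowed under POTENTIAL CHALLENGES AND SOLUTIONS, would change the group sizes by amounts the plan does not give.

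**What to change.** Amend the sentence in DATA ANALYSIS, Primary Outcomes, along these lines: enrolled and non-enrolled eligible patients are compared descriptively, by differences in proportions with Newcombe 95% intervals and by standardised mean differences with 95% intervals; where a p-value is also given for a table with any expected count below 5, it comes from an exact test (Fisher, or Fisher-Freeman-Halton for more than two categories); non-significance is not taken as evidence of similarity.

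The cost is a wording change and a different software option, with no new data. There are two drawbacks. The intervals will be wide, about ±25 to ±33 points, which is an honest account of what 12 patients can show. Exact tests are also more conservative (power 15% against 22% for 21% v 41%), so substituting them without the intervals would not solve the main problem.

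### Suicidal ideation (PHQ-9 item 9) needs a count of participants newly positive or worse, because the planned means, SDs, correlations and difference scores cannot reliably supply one

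*Combined protocol and SAP*

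**What the plan says.** The trial is a single-group proof-of-concept study with N=12. Under AIM 1: Proof-of-Concept Trial Design, the Table 2 surveys are completed at "each of the 3 timepoints (pre-intervention, post-intervention, follow-up", with follow-up at 3 months where the illness allows.

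Table 2 has separate rows for depression, "Patient Health Questionnaire – 9 Item (PHQ9", and for suicidal ideation, "Patient Health Questionnaire – Item 9 (PHQ9". The second is one item of the first.

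Under DATA ANALYSIS, Exploratory Outcomes, the purpose is given as "Within-group changes in behavioral and psychological variables will be explored to prepare for future pilot and efficacy trials". The stated summaries are: "for each data collection time points we will calculate the mean and standard deviation of exploratory outcomes"; and "we will calculate the correlation on the measures between time points as well as calculating the difference scores and the accompanying standard deviations". Frequencies and proportions appear only under Primary Outcomes, for feasibility, apart from the chi-square comparison of eligible patients who did and did not enroll.

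The AIM 1 section also provides for psychiatric referral, during the intervention, of participants whom the therapist considers at acute risk of suicide or "who demonstrate significant worsening of depression or other psychiatric comorbidities that require treatment". The documents plan no count of participants whose item 9 response became positive or increased.

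**The concern.** Item 9 is a single item with few response levels, and in 12 people most responses may well be zero. The useful question is how many participants endorse it, how many do so for the first time, and how many score higher than at baseline. A mean lets improvement in some people offset worsening in others. An SD shows spread, but neither its direction nor the number affected. A correlation does not count anyone.

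Patients with brain cancer were excluded from earlier CALM trials, so this is early information on how item 9 behaves in this population, and it feeds the next trial. A report that follows the stated analysis to the letter could leave a reader unable to tell whether anyone developed ideation.

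**Working it through.** The documents give no figure to reproduce here, so the test is whether the planned summaries determine the number who worsened.

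**Inputs.** N = 12 (AIM 1 section). Planned summaries: mean and SD at each time, between-time correlation, difference scores and their SD (Exploratory Outcomes). Item 9 scored 0 to 3: an assumption, not stated in the documents.

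**Formulas**, with x the pre score and y the post score:
- variance of x = [Σx² − (Σx)²/12]/11, and likewise for y
- covariance = [Σxy − ΣxΣy/12]/11
- variance of the difference = var(x) + var(y) − 2·cov

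All the planned group summaries therefore depend only on five sums: Σx, Σx², Σy, Σy², Σxy. Two data sets that share these sums cannot be told apart.

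**Two data sets.** Non-zero (pre, post) pairs are listed; every other participant is (0,0).

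| | Set A | Set B |
|---|---|---|
| Pairs | (1,1), (1,1), (2,0) | (0,1), (1,0), (1,0), (2,1) |
| Σx, Σx² | 4, 6 | 4, 6 |
| Σy, Σy² | 2, 2 | 2, 2 |
| Σxy | 1+1+0 = 2 | 0+0+0+2 = 2 |
| Newly positive | 0 | 1 |
| Any increase | 0 | 1 |

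**Results, the same for both sets:**
- Pre: mean 4/12 = 0.333; variance (6 − 16/12)/11 = 0.424; SD 0.651
- Post: mean 2/12 = 0.167; variance (2 − 4/12)/11 = 0.152; SD 0.389
- Covariance (2 − 8/12)/11 = 0.121; r = 0.121/(0.651 × 0.389) = 0.478
- Difference: mean −0.167; variance 0.424 + 0.152 − 0.242 = 0.333; SD 0.577

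Both sets read as a small mean improvement. In A that is the whole picture; in B it sits over one new case.

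**Is a case likely enough to matter at N = 12?** If each participant's risk of new ideation is p (assumed; the documents give none), the chance of at least one case is 1 − (1 − p)^12:

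| p | Chance of at least one case in 12 |
|---|---|
| 5% | 46% |
| 10% | 72% |
| 15% | 86% |
| 20% | 93% |

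**The case against.** Four points on the other side deserve weight.

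*The planned summaries, taken together, often do reveal worsening.* Suppose three participants go from 1 to 0 and one goes from 0 to 3. The means are 0.25 and 0.25, which looks like no change, but the SD rises from 0.45 to 0.87, the SD of change is 1.04 and r is −0.17. On a 0 to 3 scale only one data set fits. Σx = Σx² = 3 forces three baseline scores of 1; Σy = 3 with Σy² = 9 forces a single post score of 3; Σxy = 0 places that score on someone who began at 0. A reader might infer that a severe new case would vanish into the mean; in this example it would not. What stands is that recovery is not guaranteed, as Sets A and B show, and that readers should not have to solve for a count.

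*Difference scores are computed per participant.* That is so, and nothing says individual values will be withheld. But the plan names only their SDs as accompanying output, under a within-group heading, and commits to no count.

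*Individual deterioration is handled elsewhere.* The protocol has the referral route, asks participants who withdraw for their reasons, holds exit interviews covering unhelpful aspects, records reasons for attrition, and tracks additional psychological treatment and medication through follow-up. A reader might infer that ideation would go unnoticed or that the trial would give a false picture of safety. The documents do not support that: no safety conclusion is planned from Table 2, and those routes are real. They are not, however, a tabulation of item 9, and the referral wording covers only the intervention period.

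*The same complaint could be made of any scale.* Extending it to PHQ-9 and DADDS totals is largely preference. Mean change with its SD is a conventional exploratory summary for a multi-item score. For example, nine participants improving by 5 and three worsening by 6 gives −2.25 with SD 4.97, a spread that itself signals mixed directions. Nor does regression to the mean carry the argument: entry is on PHQ-9 or DADDS, so some participants are not selected on depression, and none is selected on item 9.

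**Conclusion.** The point holds for item 9 and is a modest one about reporting. Suicidal ideation is a listed outcome, and the stated summaries cannot be relied on to show how many of the 12 participants became positive or worsened. Sets A and B agree on every planned group summary but differ in the count (0 of 12 against 1 of 12). The demonstration assumes 0 to 3 scoring, and it shows that ambiguity can occur, not that it will. The 46% to 93% range rests on assumed risks. The finding does not mean that data are lost, that the clinical route is inadequate, or that the planned summaries are unsuitable for preparing later trials.

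**What to change.** In DATA ANALYSIS, Exploratory Outcomes, keep the existing summaries and add for PHQ-9 item 9:
- the number endorsing it (score ≥1) at baseline;
- at post-intervention and at 3-month follow-up, the number and percentage, out of those with data, endorsing it (≥1), newly positive (0 at baseline to ≥1), and with any increase from baseline;
- a shift table of baseline against each later time point.

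Stating N with data matters because Table 1 sets the follow-up completion target at only ≥60%, or about 7 of 12 (0.6 × 12 = 7.2). A zero count should not be over-read: 0 of 12 still has an exact one-sided 95% upper limit of 1 − 0.05^(1/12) = 22.1%.

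Optionally, report the number whose PHQ-9 total rose from baseline. A full participant listing is not needed and would carry re-identification risk in about a dozen people with a rare cancer, recruited initially at one centre.

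The cost is a sentence or two and one small table from data already collected. The drawbacks are the need for care with small cells in publication and the possibility that a less favourable result becomes visible. No change to clinical procedures is involved.
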